5.2. Inclusion Criteria

A subject will be eligible for inclusion in this study only if all of the following criteria apply:

AGE
1. ≥ 40 years of age, at the time of signing the informed consent.
TYPE OF SUBJECT AND DIAGNOSIS INCLUDING DISEASE SEVERITY
2. Hemoglobin: Stable Hgb 8.5 to 11.5 g/dL inclusive (See Section 5.1).
3. Dialysis frequency: On hemodialysis (HD, hemofiltration or hemodiafiltration) three- to five-times weekly for at least 4 weeks prior to screening.
4. Dialysis adequacy: A single pool $Kt/V_{urea} \geq 1.2$ based on a historical value obtained within the 3 months prior to screening in order to ensure the adequacy of dialysis. If Kt/V_{urea} is not available, then an average of the last 2 values of urea reduction ratio (URR) is at least 65%. NOTE: Only needs confirming at screening.
5. ESA treatment: Treated with an ESA (epoetins or their biosimilars, darbepoetin, or methoxy PEG-epoetin beta) for at least 4 weeks prior to screening.
6. Iron replacement therapy: Subjects may be on stable ($\leq 50\%$ change in overall dose and compliance of 80% of prescribed doses in the 4 weeks prior to and including the screening period) maintenance oral or IV (≤ 100 mg/week) iron supplementation. If subjects are on oral or IV iron, then doses must be stable for the 4 weeks prior to Washout.
7. Weight: Mid-week weight change between dialysis treatments $< 5\%$ as assessed post-dialysis at the Screening and Washout visits.
8. Antihypertensive Medication: Meets the following criteria: 
 • On at least 1 antihypertensive medication [excluding diuretics] 
AND
 
 • On that same medication and the same dose for at least 1 week prior to Washout

INFORMED CONSENT

9. Capable of giving signed informed consent as described in Section 10.2 which includes compliance with the requirements and restrictions listed in the consent form and in this protocol.
10. Willing and able to wear ABPM device for at least 25 hours on two separate sessions.

5.3. Exclusion Criteria

A subject will not be eligible for inclusion in this study if any of the following criteria apply:

CKD-RELATED CRITERIA

1. **Dialysis modality:** Planned change from HD to peritoneal dialysis within the study time period, or on home dialysis.
2. **Renal transplant:** Planned kidney transplant within the 16 weeks following the Screening visit.
3. **High ESA dose:** An epoetin alfa dose of ≥ 360 U/kg/week IV or ≥ 250 U/kg/week subcutaneous (SC), or darbepoetin dose of ≥ 1.8 $\mu\text{g}/\text{kg}/\text{week}$ IV or SC, or methoxy PEG-epoetin beta dose of ≥ 2.2 $\mu\text{g}/\text{kg}/\text{week}$ within the 8 weeks prior to screening through Week -4.
4. **Mircera:** Planned or recorded administration of Mircera (methoxy PEG-epoetin beta) within the 4 weeks prior to the Washout visit.

CARDIOVASCULAR DISEASE-RELATED CRITERIA

5. **Myocardial infarction or acute coronary syndrome:** Within the 3 months prior to Washout.
6. **Stroke or transient ischemic attack:** Within the 3 months prior to Washout.
7. **Heart failure:** Chronic Class IV heart failure (HF), as defined by the New York Heart Association (NYHA) functional classification system diagnosed prior to Washout.
8. **QT interval** corrected for heart rate using Bazett's formula (**QTcB**): QTcB > 500 msec, or QTcB > 530 msec in subjects with Bundle Branch Block. There is no QTc exclusion for subjects with a predominantly paced rhythm.
9. **Current uncontrolled hypertension:** Resting post dialysis systolic blood pressure > 160 mmHg; or diastolic blood pressure > 100 mmHg at screening or uncontrolled hypertension as determined by the investigator.
10. **Atrial Fibrillation:** Presence of atrial fibrillation.

OTHER DISEASE-RELATED CRITERIA

11. **Inflammatory disease:** Active chronic inflammatory disease that could impact erythropoiesis (e.g., scleroderma, systemic lupus erythematosus, rheumatoid arthritis, celiac disease) diagnosed prior to Washout.
12. **Aplasia:** History of bone marrow aplasia or pure red cell aplasia.
13. **Other causes of anemia:** Pernicious anemia, thalassemia major, sickle cell disease or

myelodysplastic syndrome.

14. Liver disease (any one of the following):

- Alanine transaminase (ALT) >2x upper limit of normal (ULN) (screening only)
- Bilirubin >1.5xULN (screening only)

NOTE: Isolated bilirubin >1.5xULN is acceptable to keep in the study if bilirubin is fractionated and direct bilirubin <35%.

- Current unstable liver or biliary disease per investigator assessment, generally defined by the presence of ascites, encephalopathy, coagulopathy, hypoalbuminaemia, esophageal or gastric varices, persistent jaundice, or cirrhosis.

NOTE: Stable chronic liver disease (including asymptomatic gallstones, chronic hepatitis B or C, or Gilbert's syndrome) are acceptable if subject otherwise meets entry criteria.

15. Major surgery: Major surgery (excluding vascular access surgery) within the 3 months prior to Washout or planned during the study.

16. Transfusion: Blood transfusion within the 8 weeks prior to Washout, or an anticipated need for blood transfusion during the study.

17. Gastrointestinal (GI) bleeding: Evidence of actively bleeding gastric, duodenal, or esophageal ulcer disease **OR** clinically significant GI bleeding within the 8 weeks prior to Washout.

18. Acute Infection: Clinical evidence of acute infection or history of infection requiring intravenous (IV) antibiotic therapy within the 8 weeks prior to Washout.

NOTE: IV antibiotics as prophylaxis are allowed.

19. Malignancy: History of malignancy within the two years prior to screening through Day 1 or currently receiving treatment for cancer, or has a known complex kidney cyst (e.g., Bosniak Category IIF, III or IV) ≥ 3 cm.

NOTE: ONLY exception is localized squamous cell or basal cell carcinoma of the skin that has been definitively treated more than 4 weeks prior to screening.

20. Blood Pressure Measurement: Subjects with an upper arm diameter which cannot be measured by oscillometer/ sphygmomanometer cuff **OR** for whom blood pressure cannot be measured in the opposite arm of current vascular access.

CONCOMITANT MEDICATIONS

21. Severe allergic reactions: History of severe allergic or anaphylactic reactions or hypersensitivity to excipients in the investigational product.

22. Drugs and supplements: Use of any prescription or non-prescription drugs or dietary supplements that are prohibited (See Section 6.11.3), from screening until Washout.

23. Prior investigational product exposure: The subject has participated in a clinical trial and has received an experimental investigational product within the 30 days prior to Day 1 or within 5 half lives of the investigational product prior to screening, whichever is longer.

GENERAL HEALTH RELATED CRITERIA

24. **Other conditions:** Any other condition, clinical or laboratory abnormality, or examination finding that the investigator considers would put the subject at unacceptable risk, which may affect study compliance or prevent understanding of the aims or investigational procedures or possible consequences of the study.
25. **Females ONLY:** Subject is pregnant [as confirmed by a positive serum human chorionic gonadotrophin (hCG) test for females of reproductive potential (FRP) only], subject is breastfeeding, or subject is of reproductive potential and does not agree to follow one of the contraceptive options listed in the List of Highly Effective Methods for Avoiding Pregnancy in Section 12.4.7.

DIAGNOSTIC ASSESSMENTS AND OTHER CRITERIA

26. **Vitamin B₁₂:** At or below the lower limit of the reference range (may rescreen in a minimum of 8 weeks, following treatment).
27. **Folate:** <2.0 ng/mL (4.5 nmol/L) (may rescreen in a minimum of 4 weeks, following treatment).
28. **Ferritin:** <100 ng/mL
29. **Transferrin saturation (TSAT):** <20%.

5.4. Screening/Baseline/Run-in Failures

Screen failures are defined as subjects who consent to participate in the clinical trial but who never enter the washout period. In order to ensure transparent reporting of screen failure subjects, meet the Consolidated Standards of Reporting Trials (CONSORT) publishing requirements, and respond to queries from Regulatory authorities, a minimal set of screen failure information is required including Demography, Screen Failure details, Eligibility Criteria, and Serious Adverse Events (see Section 7.3.1.6).

5.5. Withdrawal/Stopping Criteria

A subject may withdraw from the study at any time at his/her own request, or may be withdrawn at any time at the discretion of the investigator for safety, behavioral or administrative reasons. If a subject withdraws from the study, he/she may request destruction of any samples taken, and the investigator must document this in the site study records.

If a decision is made to withdraw a subject, he/she should return to the clinic as soon as possible to complete the Early Withdrawal assessments. The Follow-up visit should be performed 14 ± 3 days after last dose (see Time and Events Table Section 7.1).

In all cases, the reason for withdrawal from the study and date of the last dose of study treatment will be recorded in the eCRF.

5.5.1. Criteria for Permanent Discontinuation from Study Treatment and Early Withdrawal

Subjects must **permanently discontinue study treatment** and be withdrawn from the study for the following reasons:

- Meets Hgb stopping criteria (See Section 5.5.1.1)
- Receives a blood transfusion
- Receives a kidney transplant
- Becomes pregnant or intends to become pregnant during the study
- Active GI bleeding
- Diagnosis of cancer, with the exception of squamous cell or basal cell carcinoma
- Liver chemistry abnormalities exceeding the threshold criteria (See Section 5.5.3)
- Misses 2 consecutive dialysis sessions
- Use of prohibited medication (See Section 6.11.3)
- Myocardial infarction or acute coronary syndrome
- Stroke or transient ischemic attack
- New diagnosis of Class IV heart failure, as defined by the New York Heart Association (NYHA) functional classification system
- Active chronic inflammatory disease that could impact erythropoiesis
- Any new diagnosis of hematological disease including those affecting platelets, white or red blood cells, coagulation disorders, or any other cause of anemia of chronic disease other than renal disease

5.5.1.1. Hemoglobin Stopping Criteria

GSK will supply a point-of-care Hgb analyzer (HemoCue) to each site for rapid and convenient monitoring of Hgb levels and to ensure consistency of Hgb measurements across sites participating in the study.

Blood samples for measurement of Hgb concentrations via HemoCue will be collected (Table 2) and recorded in the eCRF. The table below summarizes the Hgb values and corresponding action to be taken at each visit. If the subject meets the below condition(s), then IP must be permanently stopped.

Table 2 Hgb Stopping CriteriaDay 1 (Prior to Acute Challenge 1)

Hgb at Visit	Action	
<7.5	Repeat HemoCue assessment on the same sample at same study visit to confirm; take average of 2 values. If confirmed, withdraw subject from the study.	
≥7.5-<11.5	decrease of ≥2.0 in Hgb over 2 weeks	Repeat HemoCue assessment on the same sample at same study visit to confirm; take average of 2 values. If confirmed, permanently withdraw subject from the study.
≥11.5	Repeat HemoCue assessment on the same sample at same study visit to confirm; take average of 2 values. If confirmed, avoid dosing and continue washout for one additional week. Progress with Acute Challenge 1 one week later if Hgb has decreased below 11.5; if not then withdraw subject from study.	

Days 15, 29, & 43

Hgb at Visit	Action	
<7.5	Repeat HemoCue assessment on the same sample at same study visit to confirm; take average of 2 values. If confirmed, permanently discontinue study treatment and withdraw subject from the study.	
≥7.5-<12.0	decrease of ≥2.0 in Hgb over 2 weeks	Repeat HemoCue assessment on the same sample at same study visit to confirm; take average of 2 values. If confirmed, permanently discontinue study treatment and withdraw subject from the study.

Day 57 (Prior to Acute Challenge 2)

Hgb at Visit	Action	
<7.5	Repeat HemoCue assessment on the same sample at same study visit to confirm; take average of 2 values. If confirmed, permanently discontinue study treatment and withdraw subject from the study.	
≥7.5-<11.5	decrease of ≥2.0 in Hgb over 2 weeks	Repeat HemoCue assessment on the same sample at same study visit to confirm; take average of 2 values. If confirmed, permanently discontinue study treatment and withdraw subject from the study.
≥11.5	Repeat HemoCue assessment on the same sample at same study visit to confirm; take average of 2 values. If confirmed, HOLD the dose for 1 week and progress with Acute Challenge 2 one week later. If Hgb remains above 11.5 one week later, then withdraw subject from the study.	

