6.4. Starting Dose and Dose Adjustment Algorithm

6.4.1. Subjects Randomized to Daprodustat

Subjects randomized to daprodustat will have doses adjusted, as required, to target Hgb within the range of 10.0-11.0 g/dL. Dose adjustments will be assigned **automatically** via the IVWRS based on the subject's Hgb value via onsite HemoCue assessment according to the following algorithms:

Day 1 (HemoCue Prior to Acute Challenge 1)

Hgb (g/dL)	Action or Dose
<7.5	Repeat HemoCue assessment on the same sample at same study visit to confirm; take average of 2 values. If confirmed, withdraw subject from the study.
≥7.5 and <10.0	6 mg daprodustat
≥10.0 and <11.5	4 mg daprodustat
≥11.5	Repeat HemoCue assessment on the same sample at same study visit to confirm; take average of 2 values. If confirmed, avoid dosing and continue washout for one additional week. If Hgb remains above 11.5 then withdraw subject from study.

The 8 week Hgb maintenance dosing will begin on Day 2, following Acute Challenge 1. Acute Challenge dosing is the same for all subjects on the daprodustat arm: 24 mg.

Days 15, 29, 43, & 57

The available dose steps for daprodustat are outlined below (highlighted boxes indicate starting doses). Dose adjustments will result in the daprodustat dose being increased or decreased by **one dose step**.

Hgb (g/dL)	Hgb change since previous study visit	Dose Adjustment
<7.5	Any change	Repeat HemoCue assessment on the same sample at same study visit to confirm; take average of 2 values. If confirmed, permanently discontinue study drug and withdraw subject from the study.
≥7.5 to <9.5	Decreasing or No change ¹	Increase to the next higher dose step
≥7.5 to <9.5	Increasing ²	Maintain dose

≥9.5 to ≤11.5	Any change	Maintain dose
>11.5 to <12.0	Increasing or No change	Decrease to the next lower dose step
	Decreasing	Maintain dose
≥12.0	Any change	Repeat HemoCue assessment on the same sample at same study visit to confirm; take average of 2 values. If confirmed, HOLD dosing for 2 weeks until next study visit. ³
≥7.5 to <12.0	increase of ≥1.3 in Hgb over 2 weeks ⁴	Repeat HemoCue assessment on the same sample at same study visit to confirm; take average of 2 values. If confirmed, decrease to next lower dose step,
≥7.5 to <12.0	Increase of > 2.0 in Hgb over previous 4 weeks (Days 29, 43, 57 ⁴ only)	Repeat HemoCue assessment on the same sample at same study visit to confirm; take average of 2 values. If confirmed, decrease to next lower dose step,

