¹No change is defined as an increase < 0.5 g/dL

²Increase is defined as an increase ≥ 0.5 g/dL

³ If Hgb remains ≥12.0 at next visit, the subject should be withdrawn from the study. If the Hgb drops below 12.0, the subject should be restarted on the next lowest dose.

⁴ Only applies at Day 57 if a repeat AC2 is necessary. The dose should be decreased for the 1 week between AC2 and Additional AC2.

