7.5.1.1. ABPM Delay Due to High Hgb

Day 1: If the HemoCue Hgb is confirmed to be ≥ 11.5 g/dL, then avoid dosing and continue washout for one additional week. No other assessments should be performed for that subject during the visit. When the subject returns 7 days later, re-draw the Hgb for HemoCue and assess. If confirmed to be < 11.5 g/dL then progress with the remainder of assessments and perform Acute Challenge 1. If the Hgb remains high, the subject must be withdrawn.

Day 57: If the HemoCue Hgb is confirmed to be ≥ 11.5 g/dL, then hold the dose(s) of IP for 1 week. No other assessments should be performed for that subject during the visit. When the subject returns 7 days later, re-draw the Hgb for HemoCue and assess. If confirmed to be < 11.5 g/dL then progress with the remainder of assessments and perform Acute Challenge 2. If the Hgb remains high, the subject must be withdrawn.

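### For daprodustat subjects with a confirmed Day 57 hemoglobin of 11.5 g/dL or more, Protocol 6.4.1 gives a different action from Table 2 and 7.5.1.1, and no precedence is stated

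*Protocol*

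**What the plan says.** Several places in the protocol govern a high hemoglobin at Day 57.

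- **Table 2 (5.5.1.1), both arms.** At a confirmed value of 11.5 or more: "HOLD the dose for 1 week and progress with Acute Challenge 2 one week later". At the retest: "If Hgb remains above 11.5 one week later, then withdraw subject from the study". The sentence introducing the table reads: "If the subject meets the below condition(s), then IP must be permanently stopped".
- **7.5.1.1, both arms.** At a confirmed value of 11.5 or more, "then hold the dose(s) of IP for 1 week". If the retest is below 11.5, "then progress with the remainder of assessments and perform Acute Challenge 2. If the Hgb remains high, the subject must be withdrawn".
- **6.4.1, daprodustat arm only.** The dose algorithm is headed "Days 15, 29, 43, & 57". It maintains the dose from 9.5 up to and including 11.5. Above 11.5 and below 12.0 it steps down if Hgb is rising or unchanged and maintains if it is falling. At a confirmed 12.0 or more: "HOLD dosing for 2 weeks until next study visit". Footnote 3 then withdraws the subject only if Hgb is still 12.0 or more, and otherwise restarts at the next lowest dose.
- **Footnote 4 to 6.4.1.** "Only applies at Day 57 if a repeat AC2 is necessary". It is attached only to the two rate-of-rise rows.
- **Synopsis and 4.1.** Both say that Acute Challenge 2 (AC2) may be delayed a week at 11.5 or more. Section 4.1 then refers to 7.5.1.1; the synopsis does not.
- **7.1.** Table 3 shows neither a dose adjustment nor an IVWRS entry at Day 57. Table 4, which covers Day 1 and Day 57, lists a predose IVWRS entry.

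**The concern.** Two sets of rules cover the same visit and the same measurement, and a site cannot follow both. Section 6.4.1 says that daprodustat doses are assigned automatically by the IVWRS. Which rule operates could therefore depend on how the system was programmed, while site staff working from Table 2 do something else.

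Three things are at stake:

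- how long daprodustat is withheld before the primary 6-hour SBP measurement;
- which subjects are withdrawn before AC2, and so enter only the multiple-imputation sensitivity analysis (SAP 11.1.4);
- possibly, who is in the per-protocol set, because meeting the Hgb stopping criteria is an exclusion in SAP 14.1.1 and the introduction to Table 2 leaves unclear whether a one-week hold counts as meeting them.

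The conflict with 6.4.1 exists in one arm only, so any resulting differences in dosing or withdrawal would fall on one side of the comparison.

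**Working it through.** The plan gives no figure for this point, so the check is to set the rules side by side. The rate-of-rise rows are left out because footnote 4 removes them at Day 57 unless AC2 is repeated.

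| Confirmed Day 57 Hgb (g/dL), daprodustat arm | Table 2 and 7.5.1.1 | 6.4.1 | Conflict? |
|---|---|---|---|
| 9.5 to below 11.5, without a fall of 2.0 or more over 2 weeks | no action; AC2 goes ahead | maintain | no |
| exactly 11.5 | hold 1 week, retest | maintain | yes |
| above 11.5 to below 12.0, rising or unchanged | hold 1 week, retest | step down | yes |
| above 11.5 to below 12.0, falling | hold 1 week, retest | maintain | yes |
| 12.0 or more | hold 1 week, retest; withdraw if not below 11.5 (7.5.1.1) | hold 2 weeks; withdraw only if still 12.0 or more | yes |

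**Does footnote 4 remove the conflict?** As written, no. It is not attached to the rows above 11.5. Nor do those rows fit a repeat AC2 naturally: under Table 2 a subject goes on to AC2 on Day 57 only if the predose value is below 11.5. On the confirmed predose value, the rows above 11.5 either contradict Table 2 or have no use.

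**Does the schedule settle it?** No. Table 3 suggests that no dose is assigned at Day 57, while Table 4 lists an IVWRS entry before dosing that day.

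**Related conflicts, affecting both arms:**

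- A retest of exactly 11.5 is not above 11.5, so Table 2 does not withdraw the subject. It is not below 11.5 either, so 7.5.1.1 does.
- The introduction to Table 2 requires a permanent stop when a listed condition is met, yet the row for 11.5 or more only holds the dose.
- The synopsis and 4.1 make the delay optional; Table 2 and 7.5.1.1 do not.

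**Size.** Assume that Day 57 Hgb is normal with mean 10.5, the midpoint of the 10.0 to 11.0 target range, and SD 0.7 to 1.2. The documents give neither value. The proportion at 11.5 or above is P(Z > (11.5 − 10.5)/SD):

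- SD 0.7: P(Z > 1.43) = 7.7%, and 0.077 × 25 = 1.9 subjects
- SD 1.2: P(Z > 0.83) = 20.2%, and 0.202 × 25 = 5.1 subjects

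That is about 2 to 5 of the 25 evaluable daprodustat subjects. It counts everyone in the conflicting range, not only those whose challenge or withdrawal would change.

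**Power.** The statement in 9.2.1 reproduces: 25 per arm, SD 16 and a 15 mmHg difference give 90.1% power and a half-width of 9.1 mmHg. It does not depend on this point.

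**The case against.** The best defence is that the intended reading can be worked out. The two places written for the timing of AC2, Table 2 and 7.5.1.1, agree on a one-week hold, and 4.1 sends the reader to 7.5.1.1. Table 3 ends the maintenance period at the start of AC2, and 4.1 asks subjects not to restart anemia treatment until after follow-up. A maintenance algorithm would then normally have nothing to adjust at Day 57 unless AC2 is repeated or deferred. The amendment log shows Day 57 being added to the 6.4.1 heading together with the rate-of-rise rows and footnote 4, which suggests that the repeat AC2 was in mind. The two-week hold may simply reflect the usual two-week interval between visits. Finally, withdrawn subjects are replaced (9.2.3) and early withdrawals are imputed in a sensitivity analysis.

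This makes an intended reading plausible, but it does not put that reading in the text. Footnote 4 is missing from the conflicting rows, no order of precedence is given, and a deferred AC2 is a case in which dosing during the extra week matters. Replacement restores numbers, not comparability.

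The defence does rule out some stronger readings. A reader might infer that one Hgb value can mean proceed, step down, hold one week or hold two weeks. It cannot: the step-down and two-week rows are mutually exclusive, and each value meets two conflicting actions, or three if the optional wording on delay is read as permission to go ahead. A reader might also take the instruction to maintain as an instruction to perform AC2. Section 6.4.1 sets the maintenance dose, and the challenge dose is fixed separately at 24 mg.

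**Conclusion.** The inconsistency is real and limited. From 11.5 g/dL upward at Day 57, every value in the daprodustat arm gets one action from Table 2 and 7.5.1.1 and a different one from 6.4.1. At 12.0 or more the withdrawal threshold differs as well. The conflicts over the 11.5 retest, the permanent-stop sentence and the optional delay affect both arms.

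It would go too far to say that the 6.4.1 conflict reaches the epoetin alfa arm, since 6.4.2 refers those subjects to local labelling and Table 2. It would also go too far to say that the primary result is shown to be biased: the documents do not show which rule the IVWRS applies or how many subjects reach 11.5. The estimate of 2 to 5 of 25 rests entirely on the assumed mean and SD.

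This is an internal inconsistency, not a questionable design choice. It still needs correcting, because it puts contradictory dosing instructions at the visit that supplies the primary endpoint.

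**What to change.** Reconcile the synopsis, 4.1, Table 2 with its introductory sentence, 6.4.1 with footnotes 3 and 4, 7.5.1.1, and Tables 3 and 4. Each Day 57 Hgb band, including exactly 11.5 at the retest, should have one action, stated once, with the other sections referring to it. The wording should make clear which 6.4.1 rows, if any, operate at Day 57, and whether a one-week hold counts as meeting a stopping criterion for the per-protocol set. The clinical team decides what each action is; this review proposes none.

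Then check the IVWRS programming for Day 57 against the agreed table. The cost is a wording change, by amendment or clarification letter, and a system check. Sample size and the analysis model are unaffected.
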